Sexual risk. High-risk will be defined as having unprotected vaginal or anal intercourse with a partner of unknown or HIV-positive status. Other risk factors considered will include number of partners (and number of HIV+ or unknown status) with whom one has unprotected sex, having a partner 10 or more years older or aged 35-44, experiencing IPV, social network members engage in transactional sex and/or experience IPV.

Hypothesized mediators and effect modifiers to be ascertained at each assessment include **PrEP information**-what PrEP is, common side effects, consequences of PrEP nonadherence (sample items: *most PrEP-related side effects are short-term; PrEP is highly effective in preventing HIV when taken every day*). **Perceived risk** will be assessed with the Perceived Risk of HIV scale ( $\alpha = .91$ ) (54) (sample item, *What is your gut feeling about how likely you are to get infected with HIV?*) (3), and modified to assess perceived risk for pregnancy. **Peer norms around PrEP** will be adapted from the 6-item social norm scale developed by Fernandez and colleagues ( $\alpha = .82$ ) (55) (sample items, *My partner/family would support my using PrEP*); **Positive and negative outcome expectancies of using PrEP** will be developed based on FG findings (e.g. *If I use PrEP, I will avoid conflict with my partner; my partner will object; my partner will abuse me; I will be less worried about getting HIV*), including items tapping **PrEP-related stigma** (e.g. *if I use PrEP, people will think I am promiscuous; people will think I am HIV-positive*); **PrEP attitudes**, developed from FG findings (*PrEP is a good option for me; I feel PrEP is safe to take; I feel PrEP will protect me from HIV*). **Gendered HIV prevention barriers** based on our work in a prior intervention trial (e.g., *it is the man's prerogative to use HIV protection or not; if I use HIV prevention it means I don't trust my partner; my partner could punish me*), and **self-efficacy for PrEP** (e.g., *I would be able to take the PrEP tablets every day even if I sometimes didn't feel well; if I worried that someone would see the tablets, I was short on time, I went to my boyfriend's house*). We also will assess relationship factors, including baseline experience of IPV (56), acceptability of IPV and endorsement of traditional gender norms in relationships (57). These factors may alter (modify) the effectiveness of the GE intervention.

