## Data Analysis

Workshops: Compare women randomized to the virtual group-interactive workshop with those randomized to individually-accessed links to a PrEP promotional video and PrEP information on the **primary outcome of having an individual discussion with the study nurse about the possibility of taking up PrEP; undergoing HIV self-testing guided by the study nurse (either in-person at the GHRU office or via telehealth visit) (secondary outcome); if eligible for PrEP, initiating PrEP (secondary outcome)**, and, for all women, changes in hypothesized mediators (information, risk perception, gender barriers, outcome beliefs, PrEP-stigma, peer norms) post-intervention and at 3-month follow-up.)

To compare the **primary and secondary outcomes** across the two workshop conditions, we will use generalized linear models (GLM) with a logit link function and the method of generalized estimating equations (GEE) to account for the effect of clustering within recruitment chain. The logit link function is appropriate because the primary and secondary outcomes are dichotomous and characterized as yes/no if achieved at any time over the course of the study by the time of the 3-month follow-up interview. Intervention condition (Gender-Enhanced or Individual Access) is the primary predictor. Although the original data analysis plan also specified accounting for clustering by workshop group attended, we will not account for clustering by workshop group because women in the IA condition received the intervention as individuals rather than as groups.

We will adjust for any substantial baseline differences by condition on age. We will also adjust for any substantial differences by other demographic and behavioral characteristics, such as education level, whether attending school, has a primary partner, sexual risk behaviors (to be defined), relationship power, reported intimate partner violence if these factors differ substantially by condition at baseline and are also associated with the outcome (i.e., meet the conditions of confounding).

To assess if being a PHA, i.e., talking to other women about HIV prevention serves as an additional intervention dose, a secondary analysis will include a variable for whether the woman served as a PHA and recruited other workshop attendees (yes/no).

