**Mediators.** “Other outcomes” include those measures designed to tap constructs that are hypothesized in our theoretical model to be mediators, i.e., on the pathway between the intervention and the outcome. These are factors that we believe influence the outcome (women considering PrEP for themselves) and that if changed by the intervention will lead to an increase in this outcome. We want to know if these factors are influenced by the gender-enhanced intervention and help explain (mediate) any changes in the main outcomes. These hypothesized mediators, most of which are summary measures from multi-item scales, include PrEP information, perceived risk for HIV, perceived effectiveness of PrEP, positive outcomes of taking PrEP, gendered HIV prevention barriers related to partner disclosure, PrEP-related stigma, normative beliefs, medication beliefs. Please see the related document entitled “Table of pilot study measures 2022 June 22.” for descriptions.

An additional variable—stage of change for adopting PrEP--was added when we revised the study. This will also be considered a mediator, although at 3month followup, the last option of this measure is “I am taking PrEP”. This is the indicator for the outcome of initiating PrEP.

For the mediators, we will first test if the intervention had any effect on them, using generalized linear models (GLM) with an identity link function and GEE (to account for clustering effects) to compare the mean difference between the two intervention groups from post-test to pre-test, and from 3-month follow-up to post-test, to determine if there is an increase, decrease, or no change over time (difference of difference analysis), adjusting for age and other confounders if necessary. As per [name]: the model is of the form:

$E(Y|X,T1,T2)=\text{constant}+b1*X+b2*T1+b3*T2+b4*X*T1+b5*X*T2$ , where X is the intervention indicator, T1 and T2 are post-intervention and 3-month FU indicator respectively. The regression coefficient b4 represents the group difference in change of the outcome Y (i.e., the potential mediators) from pre- to

post-intervention, however, it is b5-b4 (NOT b5) that represents the group difference in change of Y from post-intervention to 3-month FU.

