As a second step, we want to know whether, apart from the intervention, any of the hypothesized mediators are associated with the outcomes, e.g., whether women who at pre-test have low PrEP stigma, high perceived risk, low gender barriers for example, were more likely to have a nurse conversation, undergo HIV testing, initiate PrEP. These analyses will be conducted adjusting for intervention condition.

Finally, any mediators that are altered by the intervention will be included in the earlier models testing intervention effects of gender-enhanced intervention on primary study outcomes. A substantial reduction in the estimate of effect for the gender-enhanced intervention once the mediator is included in the model gives evidence that the hypothesized mediator explains in part the effect, i.e., that the intervention worked, for example, by reducing PrEP stigma or increasing risk for HIV.

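### The final mediation step omits the woman's own pre-test score, so if a later level is entered, a scale that GE shifts but that has no effect on the outcome can appear to mediate

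*SAP*

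**What the plan says.** The SAP's Data Analysis section sets out three mediation steps.

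1. Each hypothesized mediator is tested for an intervention effect with a difference-in-difference model, "to compare the mean difference between the two intervention groups from post-test to pre-test, and from 3-month follow-up to post-test". The pre-test score is used here.
2. Pre-test mediator levels are examined as predictors of the outcomes, adjusting for condition.
3. Finally, "any mediators that are altered by the intervention will be included in the earlier models testing intervention effects". The reading rule follows: "A substantial reduction in the estimate of effect for the gender-enhanced intervention once the mediator is included in the model gives evidence" that the mediator explains part of the effect. The SAP gives no threshold for substantial. It does not say whether the mediator enters as a post-test level, a 3-month level or a change.

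The earlier models are "generalized linear models (GLM) with a logit link function", fitted by GEE with clustering by recruitment chain and condition as the primary predictor. Age enters if it differs substantially by condition. Other candidates, such as "education level, whether attending school, has a primary partner, sexual risk behaviors (to be defined), relationship power, reported intimate partner violence", enter only "if these factors differ substantially by condition at baseline and are also associated with the outcome". No pre-test mediator score is among those named.

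The scores exist. Under Assessment Instruments, the Protocol has "Hypothesized mediators and effect modifiers to be ascertained at each assessment". The SAP also says of the mediators: "These are factors that we believe influence the outcome (women considering PrEP for themselves").

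**The concern.** Randomization protects the comparison of conditions. It does not protect the relation between a mediator and the outcome, because women are not randomized to their stigma or risk-perception scores. A woman who already favoured PrEP before the intervention will tend to score favourably afterwards and may also be more likely to speak with the nurse. Her pre-test score on the same scale is the most direct measure of that prior leaning.

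The covariate rule in the SAP is built to catch confounding of condition with outcome, so it asks for imbalance by condition. For the mediation step that is the wrong screen: a pre-test score can be perfectly balanced and still confound the mediator with the outcome. The mediator's coefficient then absorbs stable differences between women. Since GE has shifted the mediator, the GE coefficient falls even if changing the mediator does nothing.

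At stake is the explanation of how the workshop works, which the SAP says it wants from this analysis. The bias does not shrink with sample size.

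**Working it through.** The SAP states no figure for this step, so there is none to reproduce. The check is a simulation of the final step in which the mediator has **no** effect on the outcome.

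**Inputs from the documents.** Logistic outcome model with condition as predictor; total sample 100; comparison-arm outcome rate 20% to 50%; detectable differences of 33 to 36 points and an illustration of 85% against 50% (SAP, Power Considerations).

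**Assumed inputs (not in the documents).** Pre/post correlation r = 0.5 to 0.7; pre-test slope g = 0.3 to 1.0 log-odds per SD; GE shift in the mediator d = 0.5 to 0.8 SD. Chain clustering is left out.

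**Model.** pre ~ N(0,1); post = r·pre + d·GE + error; logit P(outcome) = a + c·GE + g·pre, with no post term. False reduction = 1 − (GE coefficient with post) / (GE coefficient without post).

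**Worked case.** a = −0.8, c = 0.8, g = 0.8, r = 0.7, d = 0.5. The GE coefficient falls from 0.703 to 0.487, and (0.703 − 0.487)/0.703 = 31%. With the pre-test score in both models it goes from 0.795 to 0.796, a reduction of 0%.

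**GE effects implied by the power section.** 50% to 85% is logit(0.85) − logit(0.50) = 1.73. From 20%, a gain of 33 to 36 points gives 53% to 56%, or 1.51 to 1.63; 1.55 was used.

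| GE effect (log-odds) | False reduction, d = 0.5 | False reduction, d = 0.8 |
|---|---|---|
| 0.8 | 9% to 39% | 14% to 66% |
| 1.55 and 1.73 | 4% to 16% | 7% to 31% |

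I reran this grid and the results agree to within about 1 point.

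**If a change score is entered.** In the same model the GE coefficient rises by 10% to 57% at c = 0.8, so no false mediation appears. But when the post-test level truly acts (logit = −0.8 + 0.4·GE + g·post, g = 0.5 and 0.8, d = 0.5), true mediation of 36% to 47% shows as only 18% to 24%.

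**If the pre-test is a noisy measure.** Here pre- and post-test are two noisy readings of prior interest, correlation 0.7, and it is prior interest that drives the outcome (g = 0.5 to 1.0, d = 0.5 to 0.8, comparison rate 50%).

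| c | False reduction, post-test level only | With pre-test score in both models |
|---|---|---|
| 0.8 | 23% to 81% | 14% to 47% |
| 1.2 | 15% to 50% | 10% to 31% |
| 1.8 | 8% to 29% | 6% to 19% |

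The change score gives about 0% throughout this version. The mechanism can be seen at c = 1.2, g = 1.0. With d = 0, adding the scale lifts the GE coefficient from 0.99 to 1.12, because odds ratios are non-collapsible. The mediator coefficient is 0.79, so at d = 0.8 one expects about 1.12 − 0.79 × 0.8 = 0.49; the fitted value is 0.49.

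**At pilot size** (n = 100, c = 1.2, r = 0.7), among runs passing a step 1 test at p < 0.05 in the GE direction, the share with a reduction of 20% or more (an assumed threshold) was as follows. The range covers the error-free and noisy versions.

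| g | d | Share |
|---|---|---|
| 0 | 0.5 | 3% to 4% |
| 0.5 | 0.5 | 23% to 29% |
| 1.0 | 0.5 | 55% to 61% |
| 1.0 | 0.8 | 85% to 93% |

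For g = 1.0 and d = 0.5, putting the pre-test score in both models lowers the share from 55% to 10% (error-free pre-test) and from 61% to 42% (noisy pre-test).

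**The case against.** - **Step 1 is a filter.** A reader might infer that any scale that merely reflects prior interest will pass as the mechanism. The documents do not support that: only altered mediators go forward. In the simulation, a scale that GE does not move passed step 1 in 2.2% to 2.4% of runs, and in large samples adding such a scale raises the GE coefficient. This stands; GE must shift the scale.
- **The form of the mediator is open.** Step 1 is framed in changes, and a change score would not produce false mediation. This also stands, but it leaves the direction of error dependent on an unstated choice.
- **The size rests on assumptions.** No g, r or d is given, and at the effects in the power section many of the false reductions are small enough that they might not be called substantial. This stands as a limit on size, not on direction.
- **The pre-test score is not a cure.** A reader might infer that adding it removes the bias. It does so only where an error-free pre-test score is the sole confounder.
- **The consequence can be overstated.** The power section carries outcome proportions and mediator means and standard deviations into the next trial, not mediation verdicts, and the reading rule claims only partial explanation. Step 2 asks whether pre-test levels predict outcomes rather than asserting it, and would make such a link visible. It would not correct step 3.

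**Conclusion.** The point holds in a conditional form. As written, the final step leaves out the pre-test score of the mediator under study, and the imbalance rule would keep out a balanced one. If a later level is entered, if GE shifts the scale, and if the pre-test level predicts the outcome, a mediator with no effect can appear to mediate. The false reduction is about 9% to 66% at a GE effect of 0.8 log-odds and about 4% to 31% at the effects used in the power section, given r of 0.5 to 0.7, g of 0.3 to 1.0 and d of 0.5 to 0.8 SD. With g = 0 it is about 0%. If a change score is entered, the false mediation does not arise, but real mediation can be understated when the pre-test score itself affects the outcome or when the later level is what matters.

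This should be changed, as a matter for a secondary analysis. Nothing here suggests bias in the primary comparison of GE with Individual Access.

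**What to change.** In the final mediation step of the SAP:

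1. State the form and time point of the mediator: its later level, measured before the outcome where possible. Outcomes count up to the 3-month interview, so a 3-month score may follow the nurse discussion.
2. Include that mediator's pre-test score in both compared models, without and with the mediator, whether or not it is balanced by condition.
3. State that this reduces but may not remove mediator-outcome confounding when the scale is a noisy measure of prior interest. Add a sensitivity analysis, such as the change-score version or a residual-confounding analysis.
4. Report the mediation result as exploratory.

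Age, sexual risk and partner violence need not be added to every mediation model; at N = 100 that is more than the data can be asked to carry.

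The cost is SAP wording, one extra covariate per model and one sensitivity analysis. No new data are needed. Women without a pre-test score drop from that analysis, and the model without the mediator should be fitted to the same women as the model with it.

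### Mediation is judged by the drop in a logit coefficient, with no interval and no fixed mediator time point, so the mediated share can be misstated in either direction

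*SAP*

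**What the plan says.** In the SAP's Data Analysis section, the binary primary and secondary outcomes are compared by "generalized linear models (GLM) with a logit link function", fitted by GEE for recruitment-chain clustering. An outcome counts if it occurs at any time up to the 3-month interview.

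The Mediators text then has three steps:

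1. Test whether the intervention changes each mediator: "compare the mean difference between the two intervention groups from post-test to pre-test, and from 3-month follow-up to post-test".
2. Ask, apart from the intervention, whether "any of the hypothesized mediators are associated with the outcomes, e.g., whether women who at pre-test have low PrEP stigma" and similar pre-test scores relate to the outcomes. "These analyses will be conducted adjusting for intervention condition".
3. Finally, "any mediators that are altered by the intervention will be included in the earlier models testing intervention effects". The reading rule is "A substantial reduction in the estimate of effect for the gender-enhanced intervention once the mediator is included in the model gives evidence" that the mediator explains part of the effect.

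No size is attached to a substantial reduction. The mediation step names no indirect-effect estimate or interval and no mediator time point. It sets no adjustment aimed at mediator-outcome confounders. The general covariate rule adds factors, age apart, only if they differ by condition at baseline and relate to the outcome, so a mediator-outcome confounder that is balanced across arms would be left out.

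Stage of change is listed as a mediator. The same text notes that its last 3-month option is the indicator for initiating PrEP.

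**The concern.** The final step compares two intervention coefficients that are not on a common scale. In a logit model, adding any strong predictor of the outcome pushes the conditional treatment coefficient away from zero, even with no mediation or confounding. That movement offsets the fall which the SAP reads as mediation.

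The open choices in the plan can work the other way. A variable that drives both mediator and outcome makes the coefficient fall too far. So does a mediator measured after the outcome, or one that contains the outcome.

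At stake is the plan's own question of whether stigma, perceived risk or gender barriers carry the intervention effect. The answer may guide what is kept for the larger study.

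**Working it through.** The documents give no figure for the mediation analysis, so there is none to reproduce. From the documents: logit link, 100 participants (about 50 per arm), and a comparison-arm rate of 20% to 50% (SAP, Power Considerations). Mediator shift, slope, direct effect and confounding are **assumptions**. All calculations ignore chain clustering.

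**1. Scale effect alone.** Let X be condition and M = aX + N(0,1), with logit P(Y) = c0 + c′X + bM. Set c0 so that the comparison rate is 30%. Integrate over M to get p00 (comparison), p10 (intervention, mediator as in comparison) and p11 (intervention, mediator shifted).

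- Drop read by the SAP = 1 − c′ / [logit(p11) − logit(p00)]
- True mediated share = (p11 − p10) / (p11 − p00)

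First case (c′=0.6, b=1, a=0.3): p00=0.3000, p10=0.4143, p11=0.4756. The marginal log-odds difference is 0.749, so the drop is 1 − 0.6/0.749 = 19.9%. The true share is 0.0613/0.1756 = 34.9%.

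| c′, b, a | Drop | True share, risk difference | True share, log odds | Gap, drop vs risk difference (points) |
|---|---|---|---|---|
| 0.6, 1.0, 0.3 | 19.9% | 34.9% | 33.1% | 15.0 |
| 0.6, 1.5, 0.3 | 20.0% | 44.6% | 42.5% | 24.6 |
| 0.6, 2.0, 0.3 | 18.4% | 51.8% | 49.6% | 33.4 |
| 0.4, 1.5, 0.5 | 51.3% | 67.0% | 64.9% | 15.7 |
| 0.6, 0.5, 0.3 (weak) | 15.5% | 21.1% | 19.9% | 5.6 |
| 0.5, 0.5, 0.5 (weak) | 29.6% | 35.0% | 33.3% | 5.4 |
| 0, 1.5, 0.5 (full) | 100% | 100% | 100% | 0 |

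In the first three rows the true share rises from 35% to 52% while the drop does not rise at all. The second row at comparison rates of 20% and 50% gives 22% against 46%, and 20% against 41%. With c′=0.6, b=1.5 and a shift of only 0.1 SD, the marginal difference is 0.537. The coefficient then *rises* by 12% (0.6/0.537) although 21% of the effect is mediated.

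**2. Forces in the other direction.** These are large-sample fits with a=0.5. Where mediation is real, b=0.7, c′=0.5 and the true share is 41%; the clean drop is 34%. In the confounded rows a common cause U loads 0.6 on M.

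| Situation | True share | Drop |
|---|---|---|
| U has log-odds slope 0.5 on Y | 41% | 51% |
| U has log-odds slope 1.0 on Y | 41% | about 70% |
| Same strong U, M has no effect on Y, c′=1.0 | 0% | 26% |
| 3-month score raised 0.8 SD by the outcome, M has no effect on Y, c′=1.0 | 0% | 40% |

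Measurement error pulls the other way: at reliability 0.7, a true 41% shows as a 24% drop.

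**3. Sampling noise.** In 2,000 simulated trials of N=100 (a=0.5, pre-post correlation 0.6), the absolute fall in the coefficient had these 95% ranges:

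- Real mediation (b=0.7, c′=0.5): −0.01 to 0.63, median 0.26.
- No mediation (b=0, c′=0.8): −0.28 to 0.20, median 0.

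**4. Step 2.** With a true post-test slope of 0.7, the pre-test score shows a slope of 0.26, 0.39 or 0.54 at pre-post correlations of 0.4, 0.6 or 0.8. At N=100 and correlation 0.6, the association is detected in about 45% of trials with pre-test scores and 88% with post-test scores.

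**The case against.** A reader might infer that the rule is always biased against mediation, so that real mediation will be understated or missed. The documents do not support this. Understatement needs partial mediation, no omitted mediator-outcome confounder, and a mediator measured before the outcome. The plan secures neither of the last two, and part 2 of the working shows drops of 26% and 40% with no mediation at all. The SAP also sets no cutoff and does not say that a small drop rules mediation out.

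A reader might also infer that the pre-test scores in step 2 remove true mediators. They do not, because entry to the final model depends on step 1. Pre-test is introduced as an example, and baseline scores can answer the question as posed. What stands is narrower: an association with "whether women who at pre-test have low PrEP stigma, high perceived risk, low gender barriers" is a baseline-predictor result and does not test the pathway.

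The large gaps need slopes of 1 to 2 log-odds per SD, that is odds ratios of 2.7 to 7.4, and no document supports such values. At 0.5 per SD (odds ratio 1.6) the gap is about 5 points, well inside the noise at N=100. The 0.1 SD example would seldom arise in practice: in a simple comparison of 50 per arm, step 1 has only about 32% power even for a 0.3 SD shift.

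Finally, Power Considerations makes feasibility, acceptability and preliminary data the main goal. That limits the consequences, but it does not make the rule informative. The overlap in part 3 is itself a reason to report an interval.

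**Conclusion.** The point holds in this form. The drop in a logit coefficient is not a sound measure of the mediated share. Under partial mediation, with nothing else biasing it, it understates that share by about 5 points for a weak mediator and by 15 to 33 points at assumed slopes of 1 to 2 log-odds per SD. It does not understate under full mediation. With omitted confounders, a post-outcome score, or stage of change as a mediator of initiation, it can overstate or create mediation. The net direction in this trial cannot be known from the documents.

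The sizes rest on assumed shifts, slopes and confounding, on a comparison rate inside the SAP's 20% to 50% range, and on ignoring clustering. The problem affects an exploratory secondary question and leaves the primary comparison untouched.

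**What to change.** Amend the Mediators text as follows:

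- In the final step, enter the **post-test** mediator score, adjusted for its pre-test score, condition and measured baseline mediator-outcome confounders, whether or not these differ by arm. The Protocol (Post intervention activities) asks about speaking with the nurse within the post-assessment and arranges the session afterwards, so this score should precede the primary outcome. Confirm this from the dates.
- Estimate the indirect effect on the **risk-difference scale** by standardising over the fitted mediator and outcome models. State the no-unmeasured-confounding assumption.
- Give a bootstrap interval that resamples whole recruitment chains. Resample within condition, because recruits join the condition of the woman who recruited them.
- Do not use 3-month stage of change as a mediator of PrEP initiation.
- Keep the pre-test analysis as a separate predictor analysis.
- Label all mediation results exploratory.

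The cost is SAP wording and modest programming, with no new data. The drawback is a wide and rather rough interval: the Protocol plans 16 seeds randomised 1:1, so about 16/2 = 8 chains per arm. Unmeasured confounding and measurement error would remain as stated limitations.
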